10. HUMAN SUBJECTS

A total of 40 patients will be recruited from the Cardiology Electrophysiology clinics of either gender for Echocardiography and AV delay optimization.

Inclusion Criteria: (all must be met)

1. Must have Symptomatic bradycardia requiring dual chamber pacemaker

2. PR interval of > 230 msec
3. Must give written informed consent
4. Must be at least 18 years old

Exclusion Criteria: (presence of any one or more)

1. Complete or high grade AV block
2. Persistent Atrial Fibrillation
3. EF < 45%
4. Patient's refusal to participate in the study

11. RECRUITMENT

Patients will be recruited from the Cardiology Electrophysiology clinic. [name] will review the potential patients' eligibility and if eligible, he or she will be consented in the clinic and will follow up as per protocol.

12. INFORMED CONSENT

Only the principal investigator or designee will obtain informed consent, after complete explanation of the nature and purpose of this study.

13. ALTERNATIVES TO STUDY PARTICIPATION

Participation in the study is voluntary, and patients may choose to not participate in this study. These patients will continue to get routine follow up as indicated for their medical condition.

14. POTENTIAL RISKS

The published literature indicates that there are no known immediate or delayed or long-term risks from ultrasound imaging using the ultrasound output levels and techniques for routine ultrasound exams.

The AV optimization involves temporary programming changes, and an electrophysiologist will be present throughout the programming. In the unlikely event that a patient does not tolerate a change in pacemaker mode, the pacemaker will be reset to its initial mode and that patient's study will be terminated.

After final programming, patients will be followed and pacemaker adjustments made as per routine clinical care. Follow up echocardiograms will be obtained to ensure there are no significant changes in cardiac function with pacing. If any changes are noted, the pacemakers will be adjusted as per routine clinical practice.

15. RISK MANAGEMENT PROCEDURES AND ADEQUACY OF RESOURCES

Patients will be monitored for any adverse events with routine clinic visits 1-2 weeks after initial implantation of the pacemaker and at 3 month intervals or as needed as per standard of clinical care. Patients will also be enrolled and followed by home remote monitoring if possible (whether or not this is possible depends on the brand of pacemaker implanted, and if they have a home telephone line).

The arrhythmia clinic is staffed by two nurse practitioners and a dedicated technician for pacemaker interrogations and related issues. We currently follow over 1,000 patients with implanted intracardiac devices. The clinic number [contact] is answered daily from 8 AM to 5 PM, and the nurse practitioners are always available during this time period. The nurse practitioners discuss all phone calls with the primary electrophysiologist and make notes into the EPIC electronic medical record.

After business hours, the answering machine provides the number for the electrophysiology fellow and attending on call, whom are available 24 hours daily for urgent issues.

There are also two research assistants in the electrophysiology division who can assist with the reporting of any adverse events to the Human Studies Committee.

The study will be funded by existing funds provided by [name] for the purpose of performing echocardiograms.

16. PRIVACY AND CONFIDENTIALITY CONSIDERATIONS INCLUDING DATA ACCESS AND MANAGEMENT

To maintain patient confidentiality, patient names and medical record numbers will be used only to retrieve (1) the final interpretation reports of the pre-pacing and post-pacing echocardiographic examinations and (2) demographic data, as described above. We will strictly maintain patient confidentiality and destroy patient identifying data immediately after data collection. Data collection forms will include only identifying research numbers—patient names, birthdates, and medical record numbers will not be used. Further, PHI will not be reused or disclosed for other purposes. All data will be kept in a locked cabinet accessible only by the principal investigator. Any data kept on a computer will be encrypted and password protected.

Patients who may have any questions or concerns can contact the principal investigator at [contact] or the HRPP

17. POTENTIAL BENEFITS

It is possible that AV delay optimization guided by echocardiography will improve cardiac output which may lead to improvement in energy levels, and quality of life.

18. RISK/BENEFIT RATIO

It is possible that AV delay optimization will improve hemodynamics with regard to cardiac output which may improve energy levels and quality of life. There is very little risk to echocardiographically optimizing the AV delay. Patients will be followed closely after pacemaker placement and programming at 2 weeks after implantation and programming and at 3 month intervals as is routine standard of clinical care. If there are any changes in clinical functional status, patients will be assessed as needed by echocardiography and any clinically indicated device programming changes will be made.

19. EXPENSE TO PARTICIPANT

There will be no added expense to enrolled subjects.

20. COMPENSATION FOR PARTICIPATION

There is no payment for participation in this study.

23. FUNDING SUPPORT FOR THIS STUDY

There are no outside sources of funding. The study will be funded by existing funds provided by [name] for the purpose of performing echocardiograms.

24. BIOLOGICAL MATERIALS TRANSFER AGREEMENT

Not applicable.

25. INVESTIGATIONAL DRUG FACT SHEET AND IND/IDE HOLDER

Not applicable.

26. IMPACT ON STAFF

All research activities will be done in the echocardiography lab by the investigators. Pacemaker management and follow up will be done as per routine standard of care.

27. CONFLICT OF INTEREST

Not applicable.

28. SUPPLEMENTAL INSTRUCTIONS FOR CANCER-RELATED STUDIES

Not applicable.

29. OTHER APPROVALS/REGULATED MATERIALS

Not needed at this time.

30. PROCEDURES FOR SURROGATE CONSENT AND/OR DECISIONAL CAPACITY ASSESSMENT

Not needed at this time.

DIVISION OF CARDIOVASCULAR MEDICINE
[contact]
NIGHTS & WEEKENDS: [contact]
[contact]

OFFICE OF:
[name].
PROFESSOR OF MEDICINE
DIRECTOR EP PROGRAM
[name]
[name]
[contact]

Date: November 15, 2024

To: Whom it may Concern

Re: Project # 130663
NCT02154750

Evaluation of AV Delay Optimization vs. Intrinsic Conduction in Patients with Long PR Intervals
Receiving Dual Chamber Pacemakers for Symptomatic Bradycardia.

Statistical Analysis Variables are displayed as the mean \pm 1SD. Categorical variables are presented as number and percentage. For comparisons of the baseline categorical variable between groups, chi-square test was used. Wilcoxon signed-rank test was used to compare each variable between baseline and 6 months after randomization. The change in each parameter was compared between each group using the Mann-Whitney U test. A p value of < 0.05 was considered statistical significance. Analyses were performed using SPSS version 23 (IBM corporation, Chicago, Illinois).

If there are any questions or concerns regarding this submission, please contact [name], Research Coordinator, at [contact]. Thank you for your consideration in this matter.

Sincerely,

A handwritten signature in black ink, appearing to read "[name]".

[name] /bb
Professor of Medicine
Director Cardiac Electrophysiology Program
University of California, San Diego

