9. RESEARCH DESIGN AND METHODS

Study Design:

This will be a randomized, prospective clinical trial. All patients enrolled will undergo echocardiographic evaluation with AV delay optimization which will be compared to intrinsic conduction, and thus patients will serve as their own controls with respect to the acute hemodynamic data.

After observing the acute hemodynamic effects of AV delay optimization vs. intrinsic conduction, patients will be randomized in a 1:1 ratio by order of enrollment to either the echocardiographically optimized AV delay vs. with a long fixed AV delay allowing for intrinsic conduction. All patients will then get follow up echocardiograms at 6 months after randomization to assess if there are any remodeling changes associated with a higher burden of RV pacing. Patients will be monitored for any adverse events with routine clinic visits one-two weeks after implantation and programming and at 3 month intervals or as needed as per standard of clinical care.

Methods:

Patients who have AV conduction with long PR intervals (>230 msec) with preserved LV function who are receiving dual chamber pacemakers for symptomatic bradycardia will be evaluated by echocardiography evaluating baseline systolic and diastolic function as well as for mechanical dyssynchrony. Baseline aortic TVI, as a surrogate of cardiac output, will be measured and will be compared with aortic TVI with AAI pacing at 70 bpm and 90 bpm and with DDD pacing 70 bpm and 90 bpm at the optimal AV delay achieved with atrio-ventricular pacing at each heart rate.

To determine the optimal AV delay, the bradycardia device will be programmed to the DDD mode, and all patients will undergo echocardiographic analysis at varying AV delays. Measurement of continuous-wave aortic Doppler flow velocities in the apical five chamber view at baseline and at eight AV intervals: 220, 200, 180, 160, 140, 120, 100, 80 ms. will be done. After 20 cardiac cycles at each AV delay, measurements will be made on the final three to four cardiac cycles and averaged. The optimal AV delay will be defined as the AV delay associated with the largest average aortic Doppler VTI.

Measurements of diastolic dysfunction and dyssynchrony will also be re-evaluated with AAI pacing and with DDD pacing at optimized AV delays to evaluate the effects of pacing on these parameters as well.

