Patients will then be randomized in a 1:1 ratio by order of enrollment to either the echocardiographically optimized AV interval or to a long-fixed AV delay that will allow for intrinsic conduction. Patients will have routine clinical follow up at 3 month intervals in the pacemaker clinic as per our usual standard of care, and then will have a comprehensive follow up 2D echo at 6 months after randomization to assess for any potential changes related to RV pacing including, RV function, LV function, LV end-systolic volume, LV end-diastolic volumes, wall thickness, and dyssynchrony as assessed by tissue Doppler imaging.

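### The between-arm test at 6 months subtracts the baseline echo value but does not adjust for it; a supplementary baseline-adjusted estimate would usually be more precise at about 20 patients per arm

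*SAP*

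**What the plan says.** The statistical paragraph of the SAP gives one between-arm outcome test: "The change in each parameter was compared between each group using the Mann-Whitney U test". Within patients, "Wilcoxon signed-rank test was used to compare each variable between baseline and 6 months after randomization", so a baseline value must exist for every variable analysed. The only stated between-group analysis of baseline is for categorical data: "For comparisons of the baseline categorical variable between groups, chi-square test was used". The threshold is given as "A p value of < 0.05 was considered statistical significance", with no statement of one- or two-sidedness.

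Protocol Section 9 has patients assessed before randomization; they "will be evaluated by echocardiography evaluating baseline systolic and diastolic function as well as for mechanical dyssynchrony". It lists six kinds of 6-month measure: RV function, LV function, LV end-systolic volume, LV end-diastolic volume, wall thickness and dyssynchrony. On allocation it says "Patients will then be randomized in a 1:1 ratio by order of enrollment". Section 10 sets the size: "A total of 40 patients will be recruited from the Cardiology Electrophysiology clinics".

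Neither document has a baseline covariate, an adjusted model or stratified randomization. Neither states power, an SD, or a correlation between baseline and follow-up.

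**The concern.** A change score assumes that one unit more at baseline predicts exactly one unit more at 6 months. Repeated echo measurements correlate below 1, so with similar SDs at the two times the true slope is less than 1 and full subtraction over-corrects. This has two consequences.

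- **Precision.** The change score carries more noise than a contrast that estimates the baseline slope.
- **Chance imbalance.** If one arm starts higher by luck, it tends to fall more through regression to the mean, and part of that fall appears as an effect of pacing mode. A chi-square test on categorical baseline variables cannot reveal a difference in volumes, function or dyssynchrony.

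The second specific aim is remodeling related to RV pacing, and this is the only comparison between randomized arms that addresses it. The sample is small and the baseline echo is already collected, so any avoidable loss of precision matters.

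**Working it through.** **Inputs from the documents.** 40 patients (Protocol Section 10) at 1:1 (Protocol Section 9) gives 40/2 = 20 per arm before any loss. Alpha is 0.05 (SAP). There is no stated power or detectable difference to reproduce.

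**Assumptions.** Two-sided test; equal SD at baseline and 6 months, used as the unit; r from 0.3 to 0.9; near-normal data unless stated.

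**Step 1: variance.** Per patient, the change score has variance 2(1 − r) and ANCOVA has 1 − r². The ratio is (1 − r²)/[2(1 − r)] = (1 + r)/2. Estimating one slope with 40 patients multiplies the ANCOVA variance by about 1 + 1/36 = 1.028.

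**Step 2: detectable difference at 80% power.** This is (1.96 + 0.842) × √(2/20) × √variance = 0.886 × √variance. At r = 0.5, change gives 0.886 × √1.00 = 0.89 SD and ANCOVA gives 0.886 × √0.75 = 0.77 SD.

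| r | Variance ratio | With covariate cost | Patients for the precision of 40 on change (40 × ratio) | Detectable: change → ANCOVA (SD) |
|---|---|---|---|---|
| 0.3 | 0.65 | 0.67 | 26 | 1.05 → 0.85 |
| 0.5 | 0.75 | 0.77 | 30 | 0.89 → 0.77 |
| 0.7 | 0.85 | 0.87 | 34 | 0.69 → 0.63 |
| 0.9 | 0.95 | 0.98 | 38 | 0.40 → 0.39 |

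**Step 3: chance imbalance.** The SE of a baseline mean difference is √(2/20) = 0.316 SD. The chance of a difference above 0.5 SD in a given variable is P(|Z| > 0.5/0.316) = 11%. Taking one variable for each of the six kinds of measure, the chance that at least one exceeds 0.5 SD lies between 11% (fully correlated) and 1 − (1 − 0.114)⁶ = 52% (independent).

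**Step 4: shift given an imbalance d.** The expected change contrast moves by (r − 1)d. For d = 0.5 SD this is −0.35, −0.25, −0.15 and −0.05 SD at r = 0.3, 0.5, 0.7 and 0.9.

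**Step 5: simulation.** Normal data, 20 per arm, 4,000 runs per setting. Power is taken at the change-score detectable difference from Step 2.

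| r | Power: Mann-Whitney on change | Power: ANCOVA | Rejection with no effect and 0.5 SD imbalance: Mann-Whitney |
|---|---|---|---|
| 0.3 | 74% | 91% | 9.5% |
| 0.5 | 76% | 88% | 8.4% |
| 0.7 | 75% | 83% | 6.8% |
| 0.9 | 76% | 79% | 5.7% |

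Given the same imbalance, ANCOVA rejects in 5.0–5.4% of runs. Over all randomizations, Mann-Whitney on change rejects a true null in 4.4–5.1% of runs, which is its nominal level.

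**Step 6: how much of the power gap is due to baseline adjustment.** A t-test on change separates the two differences between the methods. These runs use an effect of 2.88 × √[(1 − r²) × 2/20], chosen so that ANCOVA has about 80% power.

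- r = 0.7: Mann-Whitney 71%, t-test on change 74%, ANCOVA 80%. Of the 9 points, 3 come from leaving ranks and 6 from adjustment.
- r = 0.8: 74%, 77% and 79%. Of the 5 points, 3 come from leaving ranks.

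**Step 7: other distributions, same effect formula.** With lognormal data, Mann-Whitney against ANCOVA is 75% vs 76% at r = 0.8 and 76% vs 76% at r = 0.9. With heavy-tailed follow-up errors (t, 3 df) it is 79% vs 83% at r = 0.5, 88% vs 84% at r = 0.7 and 93% vs 84% at r = 0.9.

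**The case against.** The strongest reply is that nothing here is an error. Mann-Whitney on change is an accepted method, it uses the baseline value for every patient, and its false-positive rate is nominal. That stands. A reader might infer from Step 5 that the test is invalid or has an inflated error rate. The documents do not support that: the raised figures apply only given a 0.5 SD imbalance, which has an 11% chance for any one variable. Nor is it right that the plan ignores baseline; it subtracts baseline and omits it only as a covariate.

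The size of the gain is also open to challenge, and much of that stands. It depends on an r that the documents do not give. Part of the power gap reflects parametric against rank testing. With heavy tails and r of 0.7 or more, the planned test has more power than linear ANCOVA. Rank ANCOVA does not settle this: with normal data at r = 0.9 it had 70% power against 76% for the planned test.

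Finally, the SAP is dated November 2024 and written in the past tense, so the analyses appear to be complete. Replacing the documented test now would be hard to defend. This bears on how the remedy is presented, not on whether an adjusted estimate is useful.

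What the reply does not remove is that, for near-normal data and any r below 1 with equal SDs, baseline adjustment has the smaller large-sample variance and removes the shift due to chance imbalance in that variable.

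**Conclusion.** The point holds as one of precision and of bias conditional on chance imbalance, not of validity. For near-normal data with equal SDs, baseline adjustment cuts the large-sample variance by 35%, 25%, 15% and 5% at r = 0.3, 0.5, 0.7 and 0.9. At r = 0.9, after the covariate cost, only about 2% remains. The direction is secure under those assumptions; the size is not known from the documents.

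Two stronger conclusions might be inferred and should not be. One is that ANCOVA is always more powerful here: Step 7 shows otherwise, and the documents do not say how these echo measures are distributed. The other is that adjustment would secure the comparison in general. Allocation by order of enrollment may be predictable, the 5% level presumes that it behaves as random, and a single baseline covariate does not cure selection. The figure of 20 per arm is the planned maximum; the number analysed is not stated.

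**What to change.** Keep the documented Mann-Whitney test and add to the SAP, in substance:

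*For each 6-month echo variable, the arms are also compared by ANCOVA of the 6-month value on randomized arm and the baseline value of the same variable. The adjusted mean difference and its 95% CI are reported beside the Mann-Whitney result.*

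Fix any transformation for each variable, with its reason, without reference to the arm results. Do not name rank ANCOVA as a general fallback. If outcomes have been seen, label the ANCOVA a supplementary, post hoc analysis and show both results whether or not they agree.

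The cost is a few sentences and minor work in the software already named, with no new patients or echoes. It also supplies a between-arm effect estimate with an interval, which the SAP does not now specify. The small downside is reliance on a linear model with about 20 patients per arm; the retained rank test offsets this.
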